### **Auditory Tasks (with EEG recording) ( $\approx$ 2 hours, including EEG preparation):**

1. Syllable discrimination task: The task is to discriminate pairs of syllables as identical or different in three intensities of background noise. The duration of this task is approximately 10 minutes. Three hundred syllable pairs will be presented, including 150 identical and 150 different pairs. The task will be divided into three sections. For each section, participants will be asked to estimate the effort required to understand the words in the presence of background noise using a scale ranging from "no effort" to "extreme effort." Participants will be asked to respond using two keys on a computer keyboard.

### **Statistical Analyses:**

The outcome of the QuickSIN is the signal-to-noise ratio (SNR) loss. Analyses will depend on the normality of the scores. Normal: Paired-sample t-test; non-normal: Wilcoxon signed rank test.

The outcome measures for the syllable discrimination paradigm are reaction time and accuracy. We will use linear mixed-effects (LME) models separately for each dependent variable. Models will include Session (without, with) and SNR as within-subject factors. For self-reported listening effort, the listening effort score will be analyzed using a cumulative link mixed model.

Regression models with health and demographic factors will be conducted to identify predictors of the benefits.

Brain activity will be recorded using EEG. EEG recordings will be processed offline using Brain Electrical Source Analysis software (BESA 7.1). Measures of sensory-evoked response, event-related potential and connectivity will be analyzed using BESA Statistics.

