### **Study Protocol:**

This study will consist of two sessions of three hours separated by one week apart. This study will include hearing evaluations, auditory and cognitive tasks, and various questionnaires assessing health, anxiety, depression, and listening ability.

In one session, participants will perform the auditory tasks without using any hearing devices, and in the other session, participants will be fitted, under laboratory supervision, with bilateral PSAPs. The order of the two sessions will be counterbalanced across participants so that some participants will complete the tasks with PSAPs in the first session and others in the second session. Counterbalancing will be generated by randomly assigning an order to each participant using the block randomization method (three blocks).

In each session, participants will perform the same tasks. Cognitive assessment and pure-tone audiometry will be conducted only in the first session.

In each session, the participant's brain activity during the speech perception tasks will be recorded by electroencephalography (EEG) using a 76-channel Active Two acquisition system (BioSemi V.O.F., Amsterdam, The Netherlands).

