**Cognitive Assessment (≈ 20 minutes):**

1. Montreal Cognitive Assessment: General cognitive functioning will be assessed using the Montreal Cognitive Assessment Hearing Impaired (MoCA-HI), a 10-minute cognitive tool. This assessment measures several cognitive domains, including orientation, memory, visuospatial function, executive function, and language.

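### Session order is randomised, but the QuickSIN test cannot hold a visit (period) term and the listed mixed-model terms include none, so a visit effect is left in the error and costs precision.

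*Combined protocol and SAP*

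**What the plan says.** The Study Protocol section sets two sessions one week apart, one unaided and one with bilateral PSAPs. It states that "The order of the two sessions will be counterbalanced across participants", with order assigned by block randomisation in three blocks. It also says "In each session, participants will perform the same tasks" and "Cognitive assessment and pure-tone audiometry will be conducted only in the first session".

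The Statistical Analyses section then specifies:

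- **QuickSIN (SNR loss):** "Normal: Paired-sample t-test; non-normal: Wilcoxon signed rank test".
- **Syllable reaction time and accuracy:** linear mixed-effects models, for which "Models will include Session (without, with) and SNR as within-subject factors". No random effects are stated.
- **Listening effort:** "the listening effort score will be analyzed using a cumulative link mixed model". No model terms are listed.

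The section names no visit, period or order term for any outcome.

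**The concern.** The word Session has two meanings. In the Study Protocol section it is a visit; in the Statistical Analyses section its levels are without and with, so it is the device. A reader could think the visit is in the model when it is not.

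The two visits are not alike. The tasks are repeated a week later, so practice is plausible. Visit 1 also carries the cognitive assessment (about 20 minutes by its heading, 10 by its description) and pure-tone audiometry (about 10 minutes). By those durations visit 1 has 10 + 10 = 20 to 20 + 10 = 30 minutes more testing. The documents do not give the order of tests within a visit, and they do not say whether the same QuickSIN lists and syllable pairs are reused.

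In a paired analysis that ignores order, a visit effect raises the differences of people aided second and lowers those of people aided first, or the reverse. That spread is counted as noise. The Method section justifies 32 participants by comparison with other studies and not by a power calculation, so there is no documented margin to absorb a loss.

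**Working it through.** **Inputs.** From the documents: n = 32 (Method); two visits, randomised order, three blocks (Study Protocol); tests and model terms (Statistical Analyses). The plan gives no alpha, power, effect size, SD, visit effect or dropout rate, so there is no power figure to reproduce. Assumed: two-sided 5%; benefit 0.5 sd, where sd is the SD of the aided-minus-unaided difference within an order; visit effect v of 0.25 to 1.0 sd; no device-by-visit interaction.

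**Model.** In sd units, d = benefit + s·v + N(0,1), with s = +1 if aided at visit 2 (n1 people) and s = −1 if aided at visit 1 (n2 people).

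**QuickSIN, paired t-test, 16/16.** The mean of d is unbiased, but its standard error is inflated by √(1 + v²·32/31). The equivalent sample size is 32/(1 + v²·32/31). For v = 0.5: √(1 + 0.25 × 32/31) = √1.258 = 1.12, and 32/1.258 = 25.4. Power and type I error come from the normal distribution of the mean and the noncentral chi-square distribution of the sum of squares (31 df, noncentrality 32v²). The order-adjusted test is a t-test on 30 df with SE √((1/16 + 1/16)/4) = 0.177. Its power is 78.1% whatever v is.

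| Visit effect (sd) | SE inflation | Equivalent n | Power, unadjusted | Type I error, unadjusted |
|---|---|---|---|---|
| 0 | 0% | 32 | 78.2% | 5.0% |
| 0.25 | 3% | 30 | 76.3% | 4.4% |
| 0.5 | 12% | 25 | 70.5% | 2.9% |
| 0.75 | 26% | 20 | 60.7% | 1.5% |
| 1.0 | 43% | 16 | 47.7% | 0.6% |

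**QuickSIN, signed rank test, 16/16 (simulated).** Power is about 74, 67, 56 and 41% for v = 0.25, 0.5, 0.75 and 1.0. The rank-sum test on visit differences has about 75%.

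**Unequal orders.** The bias is v·(n1 − n2)/n. If each of the three blocks is balanced to within one person, block sizes summing to 32 include at most two odd sizes, so n1 − n2 is at most 2 and the worst allocation is 17/15.

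| Split | Bias as share of visit effect | Highest type I error, v = 0.25 to 1.0 |
|---|---|---|
| 17/15 | 2/32 = 6% | 4.4% |
| 16/12 | 4/28 = 14% | 4.7% |
| 17/11 | 6/28 = 21% | 5.5% |
| 16/10 | 6/26 = 23% | 5.8% |

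At 16/12 with v = 0.5 the bias is 0.07 sd. Unadjusted power there is 76.2% or 49.7% depending on the direction of the bias, against 71.3% adjusted.

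**Reaction time and accuracy.** The loss under the plan cannot be computed, because it depends on random effects that are not stated. A simulation of the remedy (32 participants, 2 sessions, 3 SNRs, 16/16) varied the share of the difference variance due to participant-by-session variation over 0, 10, 30 and 50%. Period with only a random intercept gave type I error of about 5, 6, 9 and 13%. Period with a participant-by-Device random effect held 5.0% throughout, with 78% power.

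**The case against.** The strongest case concerns importance. Randomised order already controls visit effects in the design: at balance the estimate is unbiased and the test is conservative. Losses above 10 points need a visit effect of at least 0.75 sd, which is 1.5 times the assumed benefit, and nothing in the documents supports one that large. The extra load at visit 1 is inferred from stated durations, both visits are described as three hours long, and the extra tests might come after the outcome tasks. Adjustment is not wholly free either: it pays only above a visit effect of about 0.05 sd at 16/16, and it loses a little power when there is none. For the mixed models, listing two terms does not rule out a third.

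Much of this stands. The size of the loss is unknown, the mixed-model point is silence and not exclusion, and no omission can be shown for listening effort, whose terms are not given. The inflated type I error of a random-intercept model also occurs without Period, so it is a separate gap that matters here because it affects the remedy.

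What does not fall is the QuickSIN point: the two named tests cannot use the order that the trial randomises. The break-even of 0.05 sd is trivially small.

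**Conclusion.** The concern holds. As written, the QuickSIN analysis leaves a visit effect in the error term, and the terms listed for reaction time and accuracy do not include one. At 16/16 the QuickSIN loss is negligible up to a visit effect of about 0.25 sd. It is about 8 points of power at 0.5 sd (78.1 − 70.5 = 7.6), equivalent to losing about 7 of 32 participants, and about 30 points at 1.0 sd. These figures rest on an assumed benefit of 0.5 sd and assumed visit effects.

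For QuickSIN this is a loss of precision, not a false-positive problem: bias is small at plausible splits, and type I error reaches only 5.8% even at 16/10. The same assurance cannot be given for the mixed models until their random effects are stated. The change should be made because it is cheap and can be fixed before the data are analysed, not because the planned QuickSIN test is invalid.

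**What to change.** - **QuickSIN:** analyse the aided-minus-unaided difference in a regression on order, coded +0.5/−0.5, so that the intercept is the device effect. If the data are non-normal, compare visit 2 minus visit 1 differences between the two orders with the rank-sum test.
- **Reaction time and accuracy:** rename the factor Device (without, with), add Period (visit 1, visit 2) as a fixed effect, and state a participant-by-Device random effect alongside the participant intercept. In this design that is the same as participant-by-session. Adding Period to a random-intercept-only model is not enough.
- **Listening effort:** state the terms of the cumulative link mixed model, with the same Device and Period effects.

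No new data are needed, since order is already assigned. The cost is one degree of freedom for Period and one variance component in the mixed models. With no visit effect, QuickSIN power adjusted against unadjusted is 78.1 v 78.2% at 16/16, 78.0 v 78.2% at 17/15, 71.3 v 72.3% at 16/12 and 66.3 v 68.8% at 16/10. If participant-by-session variance is truly zero, the extra random effect costs about 2 points of power (78 v 80%).

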## **Research Question and Hypothesis**

This research investigates the immediate neurobiological and behavioural effects of PSAP use on speech-in-noise performance. The specific objectives are to:

- 1) Clarify whether using PSAPs is associated with improved speech perception in noise compared to an unaided condition in individuals with normal hearing or mild to moderate hearing loss.
- 2) Determine the role of listener characteristics, such as age, sex, education, self-reported hearing loss, objective hearing loss, and cognitive status, on performance during PSAPs use.
- 3) Study the neurobiological mechanisms of benefit using electroencephalography (EEG).

Our hypotheses are twofold:

- 1) We expect that wearing PSAPs for a single session will improve performance and lower self-reported listening effort during speech-in-noise perception.
- 2) We expect that the behavioural benefits of PSAPs will be associated with increased brain activity in auditory areas and increased functional connectivity between auditory and speech regions.

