## Method

**Participants:** A total of 32 participants will be recruited. This sample size is similar to or larger than other studies examining the impact of PSAPs. Participants will be adults between the ages of 60 and 90 with normal hearing or mild to moderate hearing loss (no clinical diagnosis) who have never used hearing aids or any other type of hearing device.

Participants will be recruited through the Rotman Research Institute participant database. The selection of participants from the database will be based primarily on the hearing test results already available in the database. If necessary, additional participants will be recruited through advertisements.

Participation is voluntary and anonymous. All participants will sign a consent form before the start of the study and receive a modest stipend of \$15 per hour for their time. Reimbursement for parking fees or RTC tickets will also be provided.

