**Telephone Interview Questionnaires (≈ 45 minutes):**

1. Demographic and Health Questionnaire: This questionnaire will document demographic and health information. Information on age, gender, education level, country of birth, race, ethnicity, language, and health will be documented. This questionnaire will be completed with the participant during a telephone interview to assess eligibility. The duration of this questionnaire is approximately 30 minutes.
2. The Edinburgh Handedness Inventory: This questionnaire is a measurement scale used to assess the dominance of a person's right or left hand in everyday activities. This questionnaire will be completed with the participant during a telephone interview to determine eligibility. The duration of this questionnaire is approximately 5 minutes.

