**In-person Questionnaires (≈ 20 minutes):**

3. Speech, Spatial and Qualities of Hearing Scale (SSQ): This questionnaire measures self-perception of hearing. It consists of 49 questions divided into three sections documenting hearing abilities in different daily life situations. The questionnaire includes 14 questions on speech-related hearing disabilities, 17 questions on spatial-related hearing disabilities and 18 questions on other hearing disabilities. For each question, participants will be asked to indicate on a scale of 0 to 10 if they would be completely unable (score of 0) or perfectly able (score of 10) to perform what is described in the question (e.g., understand speech in noise). The duration of this questionnaire is approximately 10 minutes.
4. The 15-item Geriatric Depression Scale (GDS): This questionnaire is designed to detect symptoms of depression but is not used for diagnostic purposes. It consists of 15 yes/no questions about mood, aspirations, and daily activities. The duration of this questionnaire is approximately 5 minutes.
5. The 10-item Geriatric Anxiety Scale (GAS): This questionnaire is designed to detect anxiety symptoms but is not used for diagnostic purposes. It consists of 10 questions that are answered with "Not at all," "Sometimes," "Most of the time," and "All of the time." The questions also concern mood, aspirations, and daily activities, focusing on anxiety. The duration of this questionnaire is approximately 5 minutes.

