**Hearing Tests (≈ 15 minutes):**

1. Pure tone Audiometry: Pure tone audiometry will measure hearing. During this test, pure tones are sent through headphones into one ear and then into the other. This allows us to

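### The predictor regressions do not name the hearing and cognitive measures in objective 2, and they model an undefined benefit rather than the aided performance that objective 2 describes

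*Combined protocol and SAP*

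**What the plan says.** Under Research Question and Hypothesis, objective 2 is to determine the role of listener characteristics, "such as age, sex, education, self-reported hearing loss, objective hearing loss, and cognitive status, on performance during PSAPs use". That is six characteristics, given as examples, and one outcome: performance while aided.

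The Statistical Analyses section gives this objective one sentence: "Regression models with health and demographic factors will be conducted to identify predictors of the benefits". It has no variable list, no definition of benefit and no statement of which outcomes are modelled.

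The three characteristics that are not demographic each have a measure elsewhere in the protocol:

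- Self-reported hearing: the SSQ, of which the protocol says "This questionnaire measures self-perception of hearing".
- Objective hearing: "Pure tone audiometry will measure hearing", with thresholds in both ears at eight frequencies.
- Cognitive status: "General cognitive functioning will be assessed using the Montreal Cognitive Assessment Hearing Impaired (MoCA-HI), a 10-minute cognitive tool".

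Separately, the telephone interview contains a Demographic and Health Questionnaire, for which "Information on age, gender, education level, country of birth, race, ethnicity, language, and health will be documented". On size, the Method section says "A total of 32 participants will be recruited".

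**The concern.** The wording of the analysis sentence nearly matches the title of the telephone questionnaire, which is a different instrument from the SSQ, audiometry and MoCA-HI. The Study Protocol section also lists health and listening ability as separate questionnaire topics. An analyst could reasonably take the predictors from the telephone questionnaire alone. Objective 2 would then go unanswered for hearing level, which is the most obvious candidate modifier for an amplification device, and for cognitive status, which the Significance/Impact section singles out.

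The second difficulty does not depend on what health means. The objective concerns aided performance, while the analysis concerns benefit. A listener with poorer hearing may have a poor aided score and still gain the most. A report could therefore say that hearing loss predicts worse or better results, depending on a choice the plan does not make.

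Because both the predictors and the outcome are open, a reader could not tell a planned predictor result from one selected after the data were seen.

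**Working it through.** **1. Predictors: objective 2 against the analysis sentence**

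| Characteristic in objective 2 | Where measured | Covered by the analysis sentence? |
|---|---|---|
| Age | Telephone questionnaire | Yes, demographic |
| Sex | Telephone questionnaire (recorded as gender) | Yes, demographic |
| Education | Telephone questionnaire | Yes, demographic |
| Self-reported hearing loss | SSQ | Only if health includes it |
| Objective hearing loss | Pure-tone audiometry | Only if health includes it |
| Cognitive status | MoCA-HI | Only if health includes it |

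Three of the six are clearly covered. The other three depend on an undefined word.

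**2. Outcome: aided performance against benefit**

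Let A and U be a participant's aided and unaided scores, and X a predictor. Benefit is B = A − U. The slopes on X satisfy

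slope(B) = slope(A) − slope(U).

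Take a score for which higher is better and X = degree of hearing loss. If both slopes are negative but the unaided one is steeper, then slope(A) < 0 and slope(B) > 0. The same predictor is unfavourable for aided performance and favourable for benefit.

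**3. Session order**

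Each participant is unaided in one session and aided in the other, in randomised order, with the same tasks each time. Let τ be the device effect and π the practice gain from session 1 to session 2. Then

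- PSAPs in session 2: B = τ + π
- PSAPs in session 1: B = τ − π

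The two order groups differ by 2π in measured benefit for reasons unrelated to the device. Without an order term, this goes into the residual. With few participants, it can also be picked up by any predictor that happens to be unbalanced between the orders. One order term absorbs it.

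**4. What 32 participants can support**

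The sample size is justified by precedent alone, so there is no planned power figure to reproduce. The figures below assume two-sided α = 0.05, 80% power, 32 complete cases and one degree of freedom per predictor. They use the noncentral F distribution with noncentrality f² × N, and R² = f²/(1 + f²).

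- Six predictors: 32/6 = 5.3 participants per predictor; residual df 32 − 6 − 1 = 25.
- One coefficient among the six: f² = 0.27, detectable partial R² = 0.21.
- The three hearing and cognitive predictors added as a block: f² = 0.40, partial R² = 0.29.
- Overall test of all six: f² = 0.54, R² = 0.35.
- Adding session order: residual df 24; the one-coefficient figure stays at 0.21.

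Only strong associations would be found reliably. The order term costs almost nothing in detectable effect.

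**5. False positives, by scenario**

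The plan does not say how many tests will be made. For k independent 5% tests with no true association, the chance of at least one false positive is 1 − 0.95^k.

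| Scenario | k | Chance |
|---|---|---|
| One overall test for each of four outcomes | 4 | 19% |
| Three demographic predictors, four outcomes | 12 | 46% |
| Six predictors, four outcomes | 24 | 71% |

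The four outcomes are QuickSIN SNR loss, reaction time, accuracy and listening effort.

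**The case against.** The strongest reply is that the analysis sentence excludes nothing. It does not cite the telephone questionnaire. The protocol also uses health broadly: the Background calls hearing loss a chronic disability, and the Clinical Trial Registration section treats the effects under study as health outcomes. Hearing and cognitive status fit that usage. Objective 2 names both, the trial collects both, and a one-sentence summary does not bar their use.

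This stands. A reader might infer that the regressions use health and demographic factors only and leave out hearing and cognition. The documents do not support that; they show an undefined phrase with two reasonable readings.

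A reader might also infer that a false predictor is more likely than not. That does not follow either. The 71% is a conditional upper figure for 24 independent tests, an analysis the plan does not describe. Other readings give 46% or 19%, and correlation among outcomes or predictors measured on the same 32 people would make independence fail.

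It is also fair to say that neither stated hypothesis concerns listener characteristics and that searching for predictors is exploratory by nature, so formal error control is optional. The difference between sex and gender is minor wording.

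The reply does not remove the difference between aided performance and benefit, or the absence of any named hearing or cognitive measure from the analysis.

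**Conclusion.** The point holds as a mismatch between objective and analysis, not as a demonstrated omission. Three of the six characteristics in objective 2 are not named in the analysis and would go unanalysed if the phrase means the telephone questionnaire. Whether it does cannot be settled from the documents. The mismatch in outcome holds on either reading: aided performance and benefit are different quantities, and the quantity modelled is not defined.

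The precision figures (about 5 participants per predictor, detectable partial R² about 0.21) rest on assumed α, power and complete data. They support an exploratory label; they do not argue against doing the analysis. The main comparison of aided with unaided listening is not affected.

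**What to change.** In objective 2 and Statistical Analyses:

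1. Restate objective 2 as predictors of benefit, defined as aided minus unaided, and say for each outcome which direction is favourable.
2. State that the regressions include pure-tone average, SSQ score and MoCA-HI score, together with age, sex and education. Say which frequencies and ears form the pure-tone average.
3. Add the randomised session order to each model, so that practice effects are not mistaken for differences in benefit.
4. Label the analysis exploratory, given 32 participants and six predictors.

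Optional: name one key predictor and outcome, and apply a Holm adjustment to the rest. Use one term, sex or gender, in both the objective and the questionnaire.

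The cost is a few sentences, one degree of freedom per model for order (25 residual df become 24) and a less confirmatory label. The measures and the order assignment are already in the protocol, so steps 1 to 4 need no new test or visit.

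### Does hypothesis 2 go untested because the Statistical Analyses section writes out neither an aided-versus-unaided EEG contrast nor a model linking EEG change to behavioural benefit?

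*Combined protocol and SAP*

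**What the plan says.** Under Research Question and Hypothesis, the second of two hypotheses reads "We expect that the behavioural benefits of PSAPs will be associated with increased brain activity in auditory areas". It names a further EEG correlate of benefit, on the connectivity side: "increased functional connectivity between auditory and speech regions". Objective 3 in the same section concerns the neurobiological mechanisms of benefit, studied with EEG.

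The Study Protocol section has each participant attend one aided and one unaided session in randomised order, with EEG recorded during the speech tasks in both. The syllable discrimination task is the only task listed under Auditory Tasks (with EEG recording). QuickSIN is listed under Hearing Tests.

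Under Statistical Analyses, the mixed models for reaction time and accuracy have an explicit condition factor: "Models will include Session (without, with) and SNR as within-subject factors". Listening effort gets a cumulative link mixed model. Benefit is then modelled as follows: "Regression models with health and demographic factors will be conducted to identify predictors of the benefits". For EEG, the section names the processing software and adds "Measures of sensory-evoked response, event-related potential and connectivity will be analyzed using BESA Statistics".

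**The concern.** Read literally, no planned analysis contains both an EEG measure and a benefit score. The condition factor belongs to the syllable-task models, and the regression of benefit lists only health and demographic predictors. The EEG sentence names types of measure and software, but no contrast, region, time window or link to behaviour.

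The wording of hypothesis 2 makes this look serious. Its subject is the benefit, so the natural reading is that people who gain more also show a larger EEG change. Separate mean differences in EEG and in behaviour would not show that, because both can occur while the two changes are unrelated across people. One of the two hypotheses would then have no written test. With no pair of measures fixed, an association reported later could be the best of many that were tried.

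**Working it through.** **Can the text be read as covering the gap?** The condition factor follows the sentences on reaction time and accuracy, and EEG comes later in its own paragraph. The regression serves objective 2, which lists listener characteristics and no brain measure. No other section supplies an EEG-benefit model, so the omission stands.

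**Is the EEG contrast missing in substance?** The stated aim is the immediate neurobiological and behavioural effects of PSAP use. Aided versus unaided is the only manipulated difference between the sessions, and EEG is recorded in both. The effort model does not repeat the condition factor either, yet nobody would doubt that effort is compared between sessions. The contrast is implied, and terse wording is the document's style.

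**Is the association necessarily across people?** Objective 1 uses the same verb for a difference between conditions: "using PSAPs is associated with improved speech perception in noise compared to an unaided condition". If hypothesis 2 uses it that way, the implied contrast is its test. The claim that the hypothesis goes untested holds only on the across-people reading, which is the more natural one.

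**How large is the selection risk?** The syllable task has 3 outcomes (reaction time, accuracy, effort) and the plan names 3 types of EEG measure, so 3 × 3 = 9 pairs. Adding QuickSIN gives 4 × 3 = 12. Using only the two EEG constructs in hypothesis 2 gives 3 × 2 = 6. With no true association and roughly independent pairs, the chance of at least one p < 0.05 among k pairs is about 1 − 0.95^k in either direction and 1 − 0.975^k in the predicted direction. Simulation (n = 32, order-adjusted partial correlations, 20,000 runs) gives the range as the correlation within each set of measures goes from 0.7 to 0. Those correlations are assumed.

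| Pairs | Formula, either direction | Simulated | Formula, predicted direction | Simulated |
|---|---|---|---|---|
| 1 | 5% | 5% | 2.5% | – |
| 6 | 1 − 0.95^6 = 26% | 18% to 26% | 1 − 0.975^6 = 14% | 9% to 14% |
| 9 | 1 − 0.95^9 = 37% | 23% to 37% | 1 − 0.975^9 = 20% | 12% to 20% |
| 12 | 1 − 0.95^12 = 46% | 27% to 46% | 1 − 0.975^12 = 26% | 14% to 26% |

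The 9-pair row is the relevant one, because QuickSIN is not listed with EEG recording. The predicted-direction columns matter most, because hypothesis 2 is directional and a result in the opposite direction would contradict it.

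**What could a written test deliver?** The protocol gives 32 participants and no alpha or power. Assume two-sided alpha 0.05 and 32 completers, and use Fisher's z.

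- Correlation needed for 80% power: tanh((1.960 + 0.842)/√29) = 0.478, or tanh((1.960 + 0.842)/√28) = 0.485 adjusted for order.
- Power at r = 0.3, adjusted for order: Φ(0.3095 × √28 − 1.960) = 0.37.
- 95% interval around an observed r of 0, adjusted for order: ± tanh(1.960/√28) = ± 0.35.

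**The case for a change.** The strongest case for a change is that the gap exists on either reading of hypothesis 2, that it concerns half of the stated hypotheses, and that it costs little to close: a few sentences and two regressions on data already being collected. Naming one pair in advance would hold the error rate at 5% (2.5% in the predicted direction) and separate confirmatory from exploratory findings.

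Much of this stands. The omission is not explained by redaction, the selection risk exceeds the nominal rate on every count above, and choices of component, region, window and noise level would raise it further.

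The step from there to a required change is weaker. Protection comes only from fixing a particular benefit score, EEG component, region, window and connectivity metric, and from deciding whether one association or both must hold. The documents name no component or metric, so a reviewer's insertion would have to leave these blank. It would record that a test is intended, which hypothesis 2 already does, without supplying the choices that prevent selection. The gain is also modest: even a fully specified test has about 37% power at r = 0.3, and a null result would leave correlations up to about 0.35 open.

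**Conclusion.** No change follows. The Statistical Analyses section is thin on EEG, but it contains no wrong rule or number and rules nothing out. The aided-versus-unaided EEG comparison follows from the design, and the paired data for an EEG-benefit analysis will exist. Analysts working from hypothesis 2 would run both. This is missing detail of the kind that analysts fill sensibly, and the planned behavioural analyses do not depend on it.

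The remaining consequence concerns interpretation. Unless the pair of measures was fixed before the aided-versus-unaided data were examined, a reported EEG-benefit association should be read as exploratory. Across the 9 syllable-task pairs the chance of a spurious hit in the predicted direction is about 12% to 20%, against 2.5% for a single pair. A null result would not exclude a moderate association.

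These figures assume 32 completers, two-sided alpha 0.05 and correlations of 0.7 to 0 within each set of measures. The conclusion that the gap is one of specification does not depend on them.
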